10.3.1 Potential drug-induced liver injury

The number and percentage of study participants who meet one or more of the following potential drug-induced liver injury (pDILI) criteria will be summarized by treatment group and RLZ total:

- Participants with at least one post-Baseline liver laboratory assessment
- Incidence of potential hepatotoxicity with symptoms potentially associated with hepatitis or hypersensitivity
- Incidence of potential hepatotoxicity with no symptoms potentially associated with hepatitis or hypersensitivity
- Laboratory criteria for pDILI:
 - (AST or ALT > 3 x ULN) and TBL > 1.5 x ULN
 - (AST or ALT > 3 x ULN) and TBL > 2 x ULN
 - (AST or ALT > 3 x ULN) and TBL > 2 x ULN and ALP < 2 x ULN (Hy's Law)

In order to meet the above criteria, a study participant must experience the elevation in bilirubin and ALT or AST (and the absence of the ALP elevation) at the same visit. For example, a study participant who experiences a > 2x ULN elevation of bilirubin at one visit and a > 3x ULN

elevation in ALT (or AST) at a subsequent visit has not fulfilled the Hy's law criteria. If participant meets part of one criterion but at least one parameter is unknown, then he/she should not be considered for meeting the criterion.

Additional analyses for liver function tests (LFTs) will be performed to assess the potential for liver toxicities in accordance with the United States Food and Drug Administration guidelines. Per guidelines, the following criteria will be used to define levels of LFT elevation:

- Aspartate aminotransferase (AST): >3 x ULN, >5 x ULN, >8 x ULN, >10 x ULN, >20 x ULN
- Alanine aminotransferase (ALT): >3 x ULN, >5 x ULN, >8 x ULN, >10 x ULN, >20 x ULN
- AST or ALT: >3 x ULN, >5 x ULN, >8 x ULN, >10 x ULN, >20 x ULN
- Total bilirubin (TBL): >1.5 x ULN, >2 x ULN
- Alkaline phosphatase (ALP) >1.5 x ULN

A listing will also be provided for study participants who meet at least one of the above criteria. All results obtained at that visit for the specified parameters will be displayed.

10.4 Vital signs, physical findings, and other observations related to safety

10.4.1 Vital signs

Observed values and changes from Baseline will be summarized by vital signs variables (pulse rate, systolic and diastolic blood pressure, and temperature) and timepoint by treatment group.

The number and percentage of study participants who meet each of the MA criteria outlined in [Section 13.7](#) will be summarized by treatment group and RLZ total at any visit (including unscheduled visit).

A by-participant listing of all vital sign measurements and change from Baseline will be presented by treatment group and timepoint. The listing will include a flag for values identified as MA.

Repeated and unscheduled measurements will be handled as described in [Section 4.2.3](#).

10.4.2 Electrocardiograms

The following variables will be reported:

- Heart rate
- PR interval
- RR interval
- QRS duration
- QT interval
- QT corrected for heart rate using Fridericia's formula ($QTcF = QT/RR^{1/3}$)

Observed values and changes from Baseline will be summarized by treatment group and RLZ total at scheduled visit and by ECG variable. The number and percentage of study participants

with normal, abnormal not clinically significant and abnormal clinically significant ECG results will be provided in a shift table from Baseline to worst post-Baseline interpretation during the study.

For the ECG data, all calculations of changes from Baseline and descriptive statistics will be based on the mean of the triplicate assessments at each timepoint. In the event that there are not 3 available measurements at a given timepoint, the mean will be calculated based on the number of measurements for which data are provided.

The number and percentage of study participants who meet each of the MA criteria outlined in [Section 13.6](#) will be summarized by treatment group at any visit (including unscheduled visit).

A listing of electrocardiogram data will be presented, including repeated and unscheduled measurements.

10.4.3 Other safety endpoints

10.4.3.1 Physical examination

Results of physical examination abnormalities will be listed.

10.4.3.2 Suicidal risk monitoring

The C-SSRS include: (i) suicidal ideation, (ii) suicidal behavior, (iii) suicidal ideation or behavior, and (iv) self-injurious behavior without suicidal intent.

Suicidal ideation is defined as an event in any of the following 5 categories:

- [REDACTED]
- [REDACTED]
- [REDACTED]
- [REDACTED]
- [REDACTED]

Suicidal behavior is defined as an event in any of the following 5 categories:

- [REDACTED]
- [REDACTED]
- [REDACTED]
- [REDACTED]
- [REDACTED]

Suicidal behavior or ideation is defined as an event in any of the above 10 categories.

Self-injurious behavior without suicidal intent is corresponding to the response to “Has subject engaged in Non-Suicidal Self-Injurious Behavior?” in questionnaire.

A by-participant listing of the C-SSRS questionnaire data will be provided by treatment group.

10.4.3.3 Assessment and management of Tuberculosis (TB)

By-participant listings of interferon gamma release assay (IGRA) TB test, chest X-ray and TB signs and symptoms questionnaire for TB will be provided.

11 OTHER ANALYSES

11.1 Specific analyses for Pharmaceuticals and Medical Devices Agency (PMDA)

The following endpoints will be summarized for study participants in Japan only:

- Study participant characteristics (as specified in [Section 5](#))
- Demographics and other Baseline characteristics (as specified in [Section 6](#))
- Primary efficacy endpoint (as specified in [Section 8.2.2](#))
 - Change from Baseline in MG-ADL to Day 43 (Visit 10)
- Secondary efficacy endpoints (as mentioned in [Section 8.3](#)):
 - MG-ADL responder (≥ 2.0 points improvement from Baseline) at Day 43 (Visit 10)
 - Change from Baseline to Day 43 (Visit 10) in MG-C score
 - Change from Baseline to Day 43 (Visit 10) in QMG score
- Other efficacy endpoints (as mentioned in [Section 8.4](#)):
 - Use of rescue therapy due to worsening (IVIg, PEX)
 - Change from Baseline in MG-ADL at each scheduled assessment during Treatment and Observation Periods
 - In addition to the overall summary, the MG-ADL scores and change from Baseline will be summarized by the subgroup (MuSK+ or AChR+).
 - MG-ADL responder (≥ 2.0 points improvement from Baseline) at each scheduled assessment during Treatment and Observation Periods
 - Change from Baseline in QMG at each scheduled assessment during Treatment and Observation Periods
 - QMG responder (≥ 3.0 points improvement from Baseline) at each scheduled assessment during Treatment and Observation Periods
 - Change from Baseline in MG-C score at each scheduled assessment during Treatment and Observation Periods
 - MG-C responder (≥ 3.0 points improvement from Baseline) at each scheduled assessment during Treatment and Observation Periods
 - Change from Baseline in MG-QOL15r at each scheduled assessment during Treatment and Observation Periods
- ADA summaries (as mentioned in [Section 9.3.2](#)):

- Number and percentage of study participants with positive, negative or missing ADA status at the time of each visit and overall will be summarized by treatment group and RLZ total.
- Number and percentage of study participants in each of the ADA classifications will be summarized by treatment group and RLZ total.
- Number and percentage of study participants with first occurrence of treatment-emergent ADA positive at each visit will be summarized by treatment group and RLZ total.
- The cumulative number of study participants with treatment-emergent ADA positive will also be presented.
- The time to achieving treatment-emergent ADA positive, separated by treatment group and ADA category, will be analyzed based on Kaplan-Meier methods.
- The incidence of NAb, defined as (cumulative) proportion of study participants having NAb positive samples at any point up to and including that time point will be summarized by treatment group and RLZ total. Missing samples will not be included in the denominator. This will be also plotted graphically overlaying the treatment groups.
- A summary table of all immune related TEAEs by ADA status will be presented by treatment group. For this summary, study participants will be presented for TEAEs occurring prior to becoming treatment emergent ADA positive, TEAEs occurring after becoming TE ADA positive, and TEAEs for study participants who remained TE ADA negative.

Safety endpoints

The number, percentage of study participants and frequency of TEAEs will be summarized by treatment group and RLZ total. Additional details are as follows:

- An TEAE overview table will be provided, include following categories: any TEAEs, serious TEAEs, participant discontinuation due to TEAEs, permanent withdrawal of IMP due to TEAEs, temporary withdrawal of IMP due to TEAEs, treatment-related TEAEs, severe TEAEs, TEAEs leading to death, all deaths (AEs leading to death).
- Incidence of TEAE will be summarized by SOC, HLT, and PT for:
 - Any TEAEs
 - Severe TEAEs
 - Any TEAEs by maximum intensity (mild, moderate and severe)
 - Any TEAEs by relationship
 - Fatal TEAEs
 - Serious TEAEs
 - Serious TEAEs by relationship
 - Participant discontinuation due to TEAEs
 - TEAEs leading to permanent withdrawal of IMP

Treatment-emergent AESMs (Headache, Gastrointestinal disturbances and Opportunistic infections)

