Study participants who are identified as being treatment-induced or treatment-boosted ADA-positive will be grouped as treatment-emergent (TE)-ADA positive participants. Study participants who are identified as being treatment-reduced or treatment-unaffected ADA-positive will be grouped as non-TE-ADA positive participants. Both TE-ADA positive and non-TE-ADA positive participants will be further classified as NAb negative or NAb positive.

The individual and combined ADA participant categories will be summarized through the end of the 8-week observation week (Day 99), unless specified otherwise.

Table 9–1: Terms and Definitions for ADA Evaluation in Study Participants

Classification	Classification Label	Definition
Individual participant categories		
1	Pre-ADA negative – treatment induced ADA negative (ADA-NEG)	Study participants who have an ADA negative sample at Baseline and all sampling points post-Baseline up to the timepoint of interest.
2	Inconclusive	Study participants who have an ADA positive or negative Baseline sample and some post-Baseline samples are missing or inconclusive, while other post-Baseline samples are ADA negative up to the timepoint of interest.
3	Pre-ADA negative – treatment induced ADA positive (TI-POS)	Study participants who have an ADA negative sample at Baseline and have least one ADA positive sample at any sampling point post-Baseline up to the timepoint of interest.
4	Pre-ADA positive – treatment boosted ADA positive (TB-POS)	Study participants who have an ADA positive sample at Baseline and at least one ADA positive sample at any sampling point post-Baseline up to the timepoint of interest, with increased titer values compared to Baseline (greater than a predefined fold difference increase from Baseline value which will be defined within the validation of the assay i.e. MSR of the assay ^a).
5	Pre-ADA positive – treatment reduced ADA positive (TR-POS)	Study participants with an ADA positive sample at Baseline, and ADA negative samples at all sampling points post-Baseline up to the timepoint of interest.
6	Pre-ADA positive – treatment unaffected ADA positive (TU-POS)	Study participants with an ADA positive at Baseline and an ADA positive sample at any sampling point post-Baseline up to timepoint of interest with titer values of the same magnitude as Baseline (less than a predefined fold difference from the Baseline value which will be defined within the validation of the assay, i.e. MSR of the assay ^a).

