Combined participant categories		

7	Treatment emergent ADA positive (TE-POS)	Includes study participants who are treatment induced ADA positive (category 3) or treatment boosted ADA positive (category 4).
8	Non-treatment emergent ADA positive (Non-TE-POS)	Includes study participants who are treatment reduced ADA positive (category 5) or treatment unaffected ADA positive (category 6).
9	Treatment emergent ADA positive – NAb positive (TE-POS, Nab-POS)	Includes study participants who are treatment emergent positive (category 7) and have at least one NAb positive sample
10	Treatment emergent ADA positive – NAb negative (TE-POS, Nab-NEG)	Includes study participants who are treatment emergent positive (category 7) and have no NAb positive samples
11	Non-treatment emergent ADA positive-- NAb positive (Non-TE-POS, NAb-POS)	Includes study participants who are non-treatment emergent positive (category 8) and have at least one NAb positive sample
12	Non-treatment emergent ADA positive-- NAb negative (Non-TE-POS, NAb-NEG)	Includes study participants who are non-treatment emergent positive (category 8) and have no NAb positive samples

^a The fold difference increase from baseline value, i.e. the minimum significant ratio (MSR) determined during assay validation, will be reported in the relevant tables, listings and figures. It reflects the fold difference in titer level that considered higher than the assay variation in titer determination

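### SAP 11.1 splits the Kaplan-Meier analysis of time to treatment-emergent ADA positivity by a category that the event itself defines, so those curves cannot estimate incidence (Japan-only, descriptive output)

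*SAP*

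**What the plan says.** SAP Section 11.1 lists extra analyses for participants in Japan. Under ADA summaries, which it ties to Section 9.3.2, it states: "The time to achieving treatment-emergent ADA positive, separated by treatment group and ADA category, will be analyzed based on Kaplan-Meier methods". It does not say which categories are meant or at what timepoint they are fixed.

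Section 9.3.2 works with the participant categories of Section 9.3.1, Table 9-1. The relevant definitions there are:

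- The event: "Study participants who are identified as being treatment-induced or treatment-boosted ADA-positive will be grouped as treatment-emergent (TE)-ADA positive participants". These are categories 3 and 4, combined as category 7.
- Category 1 (ADA negative): "Study participants who have an ADA negative sample at Baseline and all sampling points post-Baseline up to the timepoint of interest".
- Category 2 (inconclusive): some later samples are missing or inconclusive, "while other post-Baseline samples are ADA negative up to the timepoint of interest".
- Category 3 (treatment induced): Baseline negative, and participants "have least one ADA positive sample at any sampling point post-Baseline up to the timepoint of interest".
- The horizon: "The individual and combined ADA participant categories will be summarized through the end of the 8-week observation week (Day 99), unless specified otherwise".

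Section 9.3 limits the immunogenicity evaluation to rozanolixizumab-treated participants with an evaluable Baseline sample and at least one evaluable later sample. Placebo samples are not tested for ADA.

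**The concern.** A Kaplan-Meier curve estimates how the probability of an event accumulates in a group that is at risk at time zero. The group must therefore be defined by what is known at time zero. Here it is defined by what happens later, and what happens later is the event being timed. Once participants are sorted into those who converted and those who did not, the final height of each curve is settled before any data are seen.

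At stake is the usefulness of an output specified for a regulator. A curve that reaches 100% in the TE-positive stratum could be read as an incidence. A comparison of the two doses within a category cannot show a difference in conversion rate, because that difference has gone into how many participants fall in each category.

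**Working it through.** The plan gives no sample size, rate or power for this output, so there is no figure to reproduce. The check is one of definitions, followed by a numerical confirmation.

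**Step 1: the estimator.** Cumulative incidence is F(t) = 1 − ∏(1 − d_j/n_j), where d_j is the number of events and n_j the number at risk at each event time.

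- If every member of a stratum has the event, nobody is censored. At the last event time d_j = n_j, that factor is 0, and F = 1.
- If no member has the event, every d_j is 0, the product is 1, and F = 0 throughout.

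**Step 2: each Table 9-1 category against the event, with the Day 99 default.**

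| Category | Membership requires | Members with the event | Final F |
|---|---|---|---|
| 1 | Baseline negative, all later samples negative | none | 0% |
| 2 | no positive later sample, some missing or inconclusive | none | 0% |
| 3 | Baseline negative, a later positive | all | 100% |
| 4 | Baseline positive, later titer raised beyond the assay's fold threshold | all | 100% |
| 5 | Baseline positive, all later samples negative | none | 0% |
| 6 | Baseline positive, later positive, titer not raised | none* | 0%* |
| 7 (3 or 4), with 9 and 10 its NAb subsets | TE positive | all | 100% |
| 8 (5 or 6), with 11 and 12 its NAb subsets | ADA positive but not TE | none* | 0%* |

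*Assumes that a participant with both an unchanged and a boosted positive sample is placed in category 4. Table 9-1 states no order of precedence.

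**Step 3: doses.** Let the two doses have true conversion probabilities p1 and p2. Within category 7 both curves end at 1, and within category 1 both stay at 0, for any p1 and p2. The level of the curve carries no information on p1 versus p2. Only the shape of the rise in categories 3, 4, 7, 9 and 10 carries information, and it describes onset time given conversion.

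**Step 4: numerical confirmation.** This used 20,000 simulated participants with post-Baseline ADA samples on Days 15, 24, 43, 71 and 99 (protocol Section 1.3). Illustrative assumptions were 15% positive at Baseline, each later sample 15% positive and 5% inconclusive, a fold threshold of 2, and category 4 ranked above 6.

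- Categories fixed through Day 99: categories 1 (n = 5,483), 2 (2,431), 5 (1,037) and 6 (1,078) gave F = 0. Categories 3 (9,399) and 4 (572) gave F = 1. Combined category 7 gave 1 and category 8 gave 0. Categories 9 to 12 were not simulated; their results follow because they are subsets of 7 and 8.
- The share of all simulated participants who converted was (9,399 + 572)/20,000 = 9,971/20,000 = 49.9%. No category curve shows it.
- The same data split by Baseline ADA status gave final cumulative incidences of 55.4% (Baseline negative) and 18.8% (Baseline positive). These two values depend on the assumed rates. The 0% and 100% results do not.
- Categories fixed at Day 43 with follow-up to Day 99: categories 3, 4 and 7 still reached 100%. Categories 1, 2, 5 and 6 reached 28.1%, 26.0%, 9.3% and 5.4%, all from conversions after Day 43.

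**The case against.** Four points can be made for the plan.

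**The information exists elsewhere.** A reader might infer that the plan cannot show when, or in what share of participants, ADA emerges. The documents do not support that. The same list in Section 11.1 gives the number and percentage in each ADA classification and with first TE-ADA positivity at each visit, by treatment group and rozanolixizumab total, plus the cumulative number. Section 9.3.2 gives cumulative numbers and percentages for the whole study. This stands, and it limits the point to the one curve.

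**The curves are not empty.** A reader might infer that they carry no information. In categories 3, 4, 7, 9 and 10 they describe onset time among converters, and comparing induced with boosted onset is a legitimate conditional description. This stands, provided the output is labelled that way.

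**The term is undefined.** ADA category might mean the Baseline-negative and Baseline-positive groupings that most Table 9-1 labels contain. That is possible, but Section 11.1 does not say so, and Section 9.3.2, to which it points, uses the numbered categories. If Baseline status is intended, the text still needs to state it.

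**The zeros are not unconditional.** Table 9-1 classifies up to a timepoint of interest, and an earlier cut-off would allow later events in the non-TE categories. Section 9.3.2 names Day 43 where it wants that; Section 11.1 names nothing, so Day 99 applies. The zeros in categories 6, 8, 11 and 12 also need the precedence assumption marked in the table. Both qualifications limit how absolutely the result can be stated, and neither removes it under the default.

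**Conclusion.** The point holds. With Table 9-1 categories at the Day 99 default, stratifying by ADA category conditions on the event being timed. The curves must end at 100% in categories 3, 4, 7, 9 and 10 and remain at 0% in 1, 2, 5, 6, 8, 11 and 12. They cannot estimate TE-ADA incidence over time or compare it between doses.

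This rests on three readings: that the categories meant are those of Table 9-1, that no earlier cut-off is intended, and that category 4 takes precedence over category 6. It needs no assumption about ADA rates.

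The consequence is minor. The output is descriptive and confined to Japan, with no test or decision attached. Nothing here bears on the primary or secondary efficacy analyses, or on the other ADA tables.

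**What to change.** In SAP Section 11.1, keep the split by treatment group and replace the split by ADA category with a split by Baseline ADA status (negative, positive), using the Baseline rule already in Section 9.3.1. State that the risk set is all evaluable rozanolixizumab-treated participants as defined in Section 9.3, and that participants who do not convert are censored at their last evaluable ADA sample.

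Onset time in categories 3 and 4 may be kept as a separate display if its title says that it is conditional on conversion.

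The cost is a short change of wording plus the risk-set and censoring statement. The data and the Kaplan-Meier procedure are unchanged.

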11.2 Headache questionnaire

The results of the headache questionnaire will be listed for each applicable study participant using ES. No summary tabulations will be provided for these assessments.

PUBLIC COPY
This document cannot be used to support any marketing authorization application and any extensions or variations thereof.

13 APPENDICES

13.1 QMG Scale

The QMG scale comprises 13 items, including ocular and facial movement, swallowing, speech, limb strength and forced vital capacity. Scoring for each item ranges from no weakness (0) to severe weakness (3), with an overall score range from 0 to 39, i.e., a higher score indicates more severe disease. A 3-point change in the overall score is considered to be clinically relevant.

The QMG testing form is provided in [Table 13–1](#). The total score is obtained by summing the responses to each individual item.

[figure not shown]
[REDACTED]

[REDACTED] The score ranges from 0 to 33.

[figure not shown]
In the event of missing data, the following rules will be applied:

- If 1 or 2 items are not answered, the overall score will be obtained by imputing the missing items with the average score across the remaining items at the specific visit. The imputed value will be rounded to one decimal place
- If more than 2 items are missing the overall score will not be calculated at the specific visit

Table 13–1: Quantitative myasthenia gravis testing form

This

F=female; M=male.

13.2 MG-C score

The MG-C score items and associated scores are provided in [Table 13–2](#).

The MG-C score comprises 10 items, each of which is weighted differently in the calculation of the overall score. The overall score ranges from 0 to 50, with a higher score indicating more severe disease.

[figure not shown]
The total score is obtained by summing the responses to each individual item.

The score ranges from 0 to 41.

In the event of missing data at a particular timepoint, the MG-C score will not be calculated. Due to the different weighting applied to each item it is not possible to impute the missing data with the average score across the remaining items.

Table 13–2: MG-C score items and scoring algorithm

^a Moderate weakness for head and neck items should be construed as weakness that equals roughly 50%+/-15% of expected normal strength. Any weakness milder than that would be mild and any weakness more severe than that would be classified as severe.

[figure not shown]
